## **19.0 Provisions to Protect the Privacy Interests of Subjects**

19.1 To protect privacy interest of participants, we first contact potentially eligible patients by mail. This contact includes multiple options to easily opt out of further contact: a stamped and addressed opt-out card; a toll-free telephone number to opt out of the study and an e-mail address for opting out of the study. We will wait two weeks before contacting men who have not opted out/indicated their ineligibility.

19.2 Participants will be assured of the confidentiality of their data and that their data will be carefully protected and safeguarded. Only a code number will be used to identify study-related data. Participants will be told that during the survey, they may decline to answer any questions that do not wish to answer and can leave the study at any time and for any reason.

19.3 The research team will have access to study data on password protected servers or by password protected web interfaces. Access to data will be strictly controlled.

## **20.0 Compensation for Research-Related Injury**

20.1 The risk of injury in this study is minimal.

## **21.0 Economic Burden to Subjects**

21.1 Participation in this study will not result in any additional costs for the subjects.

## **22.0 Consent Process**

22.1 We will follow the SOP: Informed Consent for Research. Consent will be obtained in one of two ways:

- 1) Print Informed Consent Document. This document will be sent to all participants. This document will be reviewed by participants and any questions that they have will be addressed during a telephone call with the study RA. Those who wish to complete the written consent can return it directly to the study team in a postage paid return envelope.
- 2) Electronic Consent. Participants who prefer to complete an electronic consent process can complete an electronic consent form immediately prior to the baseline study survey. This form is comparable to the print consent form - but adapted for electronic administration.

**Waiver or Alteration of Consent Process (consent will not be obtained, required information will not be disclosed, or the research involves deception):** Not Applicable

**Subjects who are not yet adults (infants, children, teenagers):** N/A

**Cognitively Impaired Adults:** N/A

**Adults Unable to Consent:** N/A

## **23.0 Process to Document Consent in Writing**

23.1 We will follow “SOP: Written Documentation of Consent (HRP-091).” We will obtain print or electronic consent from all participants prior to randomization. The written consent document will be sent to all participants. Those who wish to complete the written consent can return it directly to the study team in a postage paid return envelope. Participants who prefer to complete the consent form electronically can complete an electronic version of the consent form online prior to the baseline survey.

23.2 We are requesting a waiver of written consent so that participants who choose to complete the baseline study survey by telephone can complete the survey following an IRB-approved verbal consent process. Participants who we contact by telephone (who have not completed a print or electronic informed consent document), will complete an IRB-approved verbal consent process. Verbal consent will pertain only to the completion of baseline study survey. All study participants will be required to complete the print or electronic informed consent document prior to randomization. We believe this approach is justified for several reasons. First, the data collected during the baseline survey are limited to behavioral, psychosocial, attitudinal and demographic information. This survey represents minimal risk to participants. Second, with the increasing difficulty of reaching study participants by telephone, it becomes extremely important to be able to complete the baseline survey when we get a chance – rather than wait for the return of the consent documents. This process allows us to complete the minimal risk baseline survey while still requiring full informed consent prior to randomization and the delivery of the intervention. Finally, completing the survey does not in any way represent a commitment to participate in genetic counseling or testing. Participants can decline further study participation at any time.

Participants will be required to sign a clinical consent form from the testing laboratory (Invitae). This form outlines the potential benefits, limitations, and risks of genetic testing.

## 24.0 Setting

24.1 All study participants will be patients of our collaborating medical and radiation oncologists at MGUH and MWHC. Participants who are potentially eligible for the study (i.e., meet clinical genetic referral criteria) will be identified via EMR query and then contacted by the study team. All research procedures will be conducted remotely (survey completion, delivery of print genetic education and telephone genetic counseling).

## 25.0 Resources Available

25.1 *Recruiting Feasibility:* Men eligible for this study are currently being followed at MGUH or MWHC for metastatic prostate cancer or Gleason 7+ prostate cancer with a family history of breast, ovarian, pancreatic or prostate cancer or Ashkenazi Jewish ancestry. We will exclude patients who have had or are scheduled for, genetic counseling or testing. We will also exclude men who cannot participate in English and provide meaningful consent. We will recruit participants from medical and radiation oncology clinics at MGUH and MWHC (see letters of

support in attached protocol). These clinics currently follow well over 1000 eligible patients. Although we routinely attain 70% case participation, we can attain our required sample size (n=120) with much lower rates of participation.

*Time:* The project will be conducted over the next year with data analysis and manuscript preparation continuing for 1 years after the completion of participant follow-up.

*Facilities:* Participants will be contacted via mail, telephone and electronically. The study staff will initiate these contacts from the Cancer Prevention and Control office suite and from the offices of SRBSR in MGUH. Each member of the study staff has a private or semi-private office with private telephone and private secured workstations. Each office is locked and accessible only by the study staff member and the PI or Project Director. All DNA will be collected using standard DNA saliva kits used by the study participants in the privacy of their home. DNA will be shipped by mail to the designated commercial genetic testing company for preparation and sequencing in a secure and CLIA-approved facility as is standard for all clinical genetic testing samples.

*Medical and Psychological Resources:* This is a low-risk study. However, all participants will have access to a board-certified genetic counselor. All of these counselors are trained and experienced at recognizing signs of psychological distress. All positive genetic test results will be delivered by a board-certified genetic counselor who will assess psychological reactions to genetic test results and make referrals for additional services as needed. All negative or VUS results will be delivered via mailed clinical letter and will include contact information for the assigned genetic counselor in case the participant wishes to schedule a session.

*Training:* All persons involved in this research study are trained on the protocol prior to their involvement in the study. All study personnel complete standard Georgetown University Human Subjects Training through the CITI program. All staff are supervised directly by the PI and participate in weekly study meetings. Further, procedures for ensuring data integrity and security will be reviewed at regular intervals throughout the study. Ethical issues and topics related to the responsible conduct of research will also be discussed routinely with the overall study team, including the potential for adverse events, data safety and data management, handling misconduct, etc.

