Despite these benefits and existing referral guidelines, few men with prostate cancer are tested. This reflects low genetic counseling referral and participation, since men who attend genetic counseling get tested at the same high rate as women. Low participation in genetic counseling is likely due to men's underestimation of the personal health relevance of testing and lack of physician genetic counseling referral. Thus, the requirement to obtain individual genetic counseling prior to genetic testing may be a barrier to the receipt of guideline consistent genetic testing. In fact, recent evidence suggests that traditional comprehensive, patient-centered, educationally focused pre-test genetic counseling often does not match the needs of patients. Further, as genetic referral guidelines continue to expand, demand for genetic counseling will outstrip delivery capacity. Thus, alternative approaches that raise awareness and facilitate access to genetic testing are needed to maximize our ability to extend the benefits of testing to prostate cancer patients and their family members while at the same time accommodating increased demand and conserving scarce genetic counseling resources.

In the proposed pilot, we will develop and test a proactive and streamlined pre-test genetic education (ST) print intervention designed to speed, simplify and target genetic testing delivery for prostate cancer patients. Participants randomized to ST will have the option to proceed directly to genetic testing bypassing traditional pre-test genetic counseling. In contrast, usual care (UC) participants will be informed that they meet guidelines for genetic counseling referral and will be provided with contact information to schedule a standard telephone pre-test genetic counseling session. All participants with a PV or variant of uncertain significance (VUS) will be scheduled for a telephone genetic counseling disclosure session. ST participants who are found not to carry a PV or VUS will have this result disclosed via clinical letter while disclosure for all UC participants will be per standard clinical care by the genetic counselor by phone. By proactively identifying eligible patients, providing streamlined information and facilitating genetic testing, the ST intervention will increase awareness, facilitate informed testing decisions, remove the barrier of pre-test genetic counseling and improve genetic testing delivery capacity.

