## **5.0 Study Intervention/Investigational Agent**

The streamlined testing (ST) intervention includes: proactive identification and contact of patients eligible for genetic services, streamlined pre-test genetic education, facilitated delivery of genetic testing, targeted genetic counseling disclosure for patients with a PV or variant of uncertain clinical significance (VUS) and a clinical disclosure letter for patients who do not carry a PV. We have developed a range of media for cancer risk communication, including print, electronic and in-person education. The ST print materials will include the following topics: 1) Introduction and explanation of genetic testing guidelines for prostate cancer patients; 2) Explanation of panel testing and potential genetic testing outcomes (positive, negative, uncertain variant); 3) Personal implications of a PV (cancer risks associated with a positive genetic testing result; treatment/management, risk management for second cancers); 4) Implications for family members; 5) Legislation to protect against genetic discrimination; 6) Process of genetic testing: DNA collection (saliva kit), costs, and insurance coverage; 7) Options for and logistics of genetic counseling: pre-test counseling is optional unless required by insurance; post-test genetic counseling for all positives (no charge for telephone genetic counseling). Drawing on our prior work, the ST materials will include text, images, illustrations and graphics. We expect that the material will take 10-15 minutes to review. *Participants randomized to the usual care (UC) arm will be sent a letter from their physician indicating that they meet eligibility criteria for genetic counseling and recommending that they schedule genetic counseling. UC participants can receive free telephone genetic counseling through the study.*

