## **6.0 Procedures Involved\***

6.1-6.4 The objective is to develop and pilot a novel streamlined approach to deliver genetic education and testing to the rapidly increasing number of prostate cancer patients who meet guidelines for genetic referral. Our streamlined genetic testing approach is designed to facilitate genetic education and testing for men with prostate cancer. The intervention will incorporate proactively delivered print educational materials in lieu of pre-test genetic counseling. The materials will increase awareness, expand access, provide

balanced information to foster informed genetic testing decisions and reduce barriers to facilitate the delivery of genetic testing. All men who are found to carry a PV or variant of uncertain significance (VUS) in a cancer risk gene will have an individual telephone genetic counseling disclosure session with a board-certified genetic counselor. We will recruit 120 prostate cancer survivors who meet clinical referral criteria. After a baseline survey, we will randomize participants to: ST vs. UC. Participants will complete a follow-up survey at 2-3-months post-randomization. Our primary outcome is genetic testing uptake.

Eligibility and Accrual. Men eligible for this study are currently being followed at MGUH or MWHC for either:

Metastatic prostate cancer;  
Gleason 7+ prostate cancer.

We will exclude patients who have had, or are already scheduled for genetic counseling or testing for *BRCA1* or *BRCA2* mutations. We will also exclude men who cannot participate in English and provide meaningful consent. We will recruit participants from medical and radiation oncology clinics at MGUH and MWHC. These clinics currently follow well over 1000 eligible patients.

Gender and Minorities. Participants will be adult men. Given the racial/ethnic breakdown of the clinics we are recruiting from. We expect that at least 30% of participants will be members of racial/ethnic minority groups.

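### Section 25.1 mails all VUS and negative results, while sections 2, 5, 6, 8.1 and 15 put VUS results in a counselling session and section 2 gives all UC results by phone

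*Combined protocol and SAP*

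**What the plan says.** Section 25.1, under medical and psychological resources, first says that a board-certified counselor delivers positive results. It then says: "All negative or VUS results will be delivered via mailed clinical letter". The letter is to "include contact information for the assigned genetic counselor in case the participant wishes to schedule a session", so any session is at the man's request. The sentence names no arm.

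Other sections give a different route:

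- Section 2.0: "All participants with a PV or variant of uncertain significance (VUS) will be scheduled for a telephone genetic counseling disclosure session". It limits the letter to ST men with neither a PV nor a VUS, and adds that "disclosure for all UC participants will be per standard clinical care by the genetic counselor by phone".
- Section 5.0 includes in the ST intervention "targeted genetic counseling disclosure for patients with a PV or variant of uncertain clinical significance (VUS").
- Section 6.1-6.4: men with a PV or "variant of uncertain significance (VUS) in a cancer risk gene will have an individual telephone genetic counseling disclosure session".
- Section 8.1 has a counselor contact men with a positive or VUS result, in either arm, to arrange a telephone disclosure session. It names only ST men for mail notification of a negative result and does not mention UC negatives.
- Section 15.1 says twice, in the distress plan and in reason C for low risk in ST, that men with a PV or VUS have a counselling disclosure session. It does not say whether by telephone.

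**The concern.** Staff following the protocol have two incompatible instructions for the same result. The consequences differ by result type.

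**VUS results.** Section 15.1 relies on the disclosure session in two places: the counselor assesses distress and coping there, and the session is one of four reasons (A to D) why skipping pre-test counselling is considered low risk. Under section 25.1 the VUS part of both would not hold. An ST man with a VUS who never asks for a session would have no counselling before or after testing. Other protections remain: reasons A, B and D, the PV part of C, free counselling on request, and referral of men who report high distress on a survey.

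**Negative results.** Under section 2.0 the route differs by arm (letter in ST, phone in UC). Under section 25.1 it does not. Distress, decision satisfaction and regret are measured at T1, 2 to 3 months after randomization, so disclosure may come before them. Aim 2 is meant to supply effect sizes for the planned larger trial, so readers need to know which contrast was delivered. The documents give no basis for sizing any effect on these measures.

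**Working it through.** No figure in the plan rests on the disclosure route, so the check is a comparison of text, followed by a count of the men affected.

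**Routes side by side**

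| Section | PV | VUS | Negative, ST | Negative, UC |
|---|---|---|---|---|
| 2.0 | telephone session, all | telephone session, all | letter | counselor by phone |
| 5.0 (ST only) | counselling disclosure | counselling disclosure | letter | not applicable |
| 6.1-6.4 | telephone session | telephone session | not stated | not stated |
| 8.1 | telephone session, either arm | telephone session, either arm | mail, session on request | not stated |
| 15.1 | counselling session | counselling session | not stated | not stated |
| 25.1 | counselor | **letter, session on request** | letter, session on request | **letter, session on request** |

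The VUS column sets section 25.1 against five sections. The UC-negative column sets it against one sentence in section 2.0. PV results and ST negatives are consistent throughout.

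Reading 25.1 as a letter in addition to a session does not remove the VUS conflict. That section makes the letter the means of delivery and the session optional, whereas reason C in section 15.1 has the man receive the result within the session.

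Three other phrases leave the VUS route unclear without contradicting the session. Section 5.0 describes "a clinical disclosure letter for patients who do not carry a PV", which read literally includes men with a VUS. Topic 7 of the ST print materials lists "post-test genetic counseling for all positives (no charge for telephone genetic counseling") and does not mention VUS. Section 3.0 speaks of directing counselling to men with a PV result.

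**Men affected**

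Inputs: 120 men randomized 1:1 (section 6), so 60 per arm; design uptake of 45% in ST and 20% in UC, and the Table 2 ranges of 40-50% and 10-20% (section 17.1); PV frequency of up to 17% (section 3.0).

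- Tested at design: 60 × 0.45 = 27 ST and 60 × 0.20 = 12 UC, together 39.
- Tested over Table 2: ST 60 × 0.40 = 24 to 60 × 0.50 = 30; UC 60 × 0.10 = 6 to 60 × 0.20 = 12; together 30 to 42.
- Untested, with no result to disclose: 120 − 39 = 81 (67.5%); over Table 2, 78 to 90 (65% to 75%).
- ST, where only VUS is in conflict: each 10 points of VUS rate is 27 × 0.10 = 2.7 men (2.4 to 3.0 over Table 2). The documents give no VUS rate. An assumed 10% to 40% gives 27 × 0.10 = 2.7 to 27 × 0.40 = 10.8 men.
- UC, where VUS and negatives are both in conflict, so no VUS rate is needed: 12 × (1 − 0.17) = 9.96, about 10 of 12; at 10% uptake, 6 × 0.83 = 4.98, about 5 of 6. With no PV found, all 12 or all 6.

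**The case against.** The best defence is that this is a drafting slip. The sentence sits in a resources section, while section 8.1, which is dedicated to returning results, states the VUS route clearly for either arm, and four other sections agree. The primary outcome and sample size are untouched, about two thirds of the men have no result to disclose, and Aim 2 is mainly for estimation in a pilot, so any effect on T1 measures is speculative. All of that is correct and limits the weight of the point. It does not remove the conflict: the sentence is an operative instruction under psychological resources, and nothing in the protocol gives one section precedence.

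Three further objections stand in part:

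- The larger UC count consists of VUS and negative results together, and for the negatives the conflict is the thin one. UC men are also directed to pre-test counselling, so having no counselling before or after testing is an ST concern. For the ST men concerned, the number rests on an assumed VUS rate.
- The 17% figure describes men with prostate cancer generally. Applying it to this referral group is an assumption, and the results are expected counts. Section 3.0 says of referred patients only that most carry no PV.
- The phrases in sections 3.0 and 5.0 are matters of clarity, and the ST print text is not in the documents, so what it tells men about a VUS cannot be judged.

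**Conclusion.** The concern holds. Section 25.1 contradicts sections 2.0, 5.0, 6, 8.1 and 15.1 on VUS results, and contradicts section 2.0 on negative results in UC. It should be fixed, mainly because the VUS part of the section 15.1 safeguards depends on which text is followed, and secondly because the disclosure contrast between the arms does too.

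The numbers are small: roughly 3 to 11 of 27 tested ST men if the VUS rate is 10% to 40% (assumed), and about 10 of 12 tested UC men if 17% carry a PV (assumed to apply here). The uptake comparison and its power do not change. The existence of the conflict depends on none of these assumptions. This review takes no position on which disclosure rule is right.

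**What to change.** Reconcile section 25.1 with sections 2.0, 5.0, 6, 8.1 and 15.1 so that the protocol states one disclosure route for each result type (PV, VUS, negative) in each arm. Include UC negatives in section 8.1, which now omits them. The investigators and the IRB choose the rule. Then bring these into line with it:

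- the distress plan and reason C in section 15.1;
- the description of the arms in section 2.0;
- the letter group and print topic 7 in section 5.0.

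The cost is a minor wording amendment and a check of what the ST print materials say about post-test counselling. No extra data are needed.

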## **26.0 Multi-Site Research\***

*26.1* This is not a multisite study.
